Appendix 2: Participant follow-up Questionnaire (Part-Quest-Follow-up)

11. What is the cause for your current MSK pain (ex. a fall, a hit or other)? (If you are familiar with it)

12. How long does a pain episode usually last?

- Less than 3 hours
- Less than 24 hours
- 1-7 days
- Longer than 7 days

13. How often do you have a pain episode?

- I don't have breaks from the pain
- At least once a week
- Less than once a week

14. How often do you feel nervous?

- Often/sometimes
- Seldom/never

15. How large a part of your friends have immigrant background?

- None
- Almost none
- Almost all
- All

16. Outside school hours, how many hours a day do you spend watching TV/tablet/mobile phone/computer or do other activities when mostly sitting down? _____ hours/day

17. Are you physical active besides school hours?

- Yes - how many times per week are you physical active besides mandatory physical education during school hours? _____
- No

18. Do you smoke cigarettes?

- Yes - how many cigarettes a day? less than 1 1-4 5-9 more than 9
- No

19. Do you expect to be pain free in the future?

- Yes, in the near future
- Yes, in the long term future
- No

20. Why did you come to your doctor today? You may choose more than one answer with circles.

- I want my pain to stop
- I am worried about the cause of my pain
- My family made me come
- I have a personal problem
- Because of my pain, I can't use my body as I used to

21. Do you expect your doctor to give you medication for your pain?

- Yes, I would like that
- No, I don't think so
- I don't know

22. If you have a job, what do you do _____ and how many hours do you work on a weekly basis? _____

In the following last questions mark "x" in either yes or no

Does your pain make any of the following activities difficult?	Yes	No
-reaching up to get a book from a high shelf		

Appendix 2: Participant follow-up Questionnaire (Part-Quest-Follow-up)

	Yes	No			
			-carrying your school bag to school		
Is your pain radiating to your legs or arms?			-sitting on a school chair for a 45 min. lesson		
Do you feel anxious?			-standing in a queue for 10 min		
Do you think that you have low self-esteem?			-sitting up in bed from a lying position		
Do you believe in God?			-bending down to put your socks on		
Is it difficult to fall asleep because of pain?			-standing up from an armchair at home		
Is it difficult to sit during a lesson?			-running fast to catch a bus		
Does your pain disturb a walk longer than 1 km?			-sport activities at school		
Does your pain disturb your physical exercise?					
Does your pain disturb your hobbies?					
Do you have pain outside school hours					
Are you tired during the day?					
Do you feel depressed?					

Appendix 3: Parent Questionnaire (Pare-Quest)

1. What is your relation to the child? (58)
 - Mother
 - Father
 - Other
2. What is your biological relation to your child?
 - Biological parent
 - Stepparent
 - Adoptive parent
3. How old are you? _____
4. What are your living arrangements with your child?
 - My child does not live with me
 - My child lives with me part time
 - my child lives with me full time
5. What is your relationship status with your child's other parent?
 - I am married to my child's other parent
 - I live with my child's other parent outside marriage
 - I am separated/divorced from my child's other parent/we don't live together
6. Where were you born? (58)
 - Denmark
 - Other – where? _____ and how many months/years have you lived in Denmark? _____
7. Do you smoke cigarettes? yes / no
8. Have you experienced chronic pain of more than 6 months, associated with arthritis, migraine, cancer, stomach ulcers or in your muscles, bones or tendons? (59) yes / no
9. Has one or more of your child's siblings had pain in their muscle, joint, bone or tendon? yes / no
10. Do you take pain killers, when you feel pain? yes / no
11. What do you feel the most as?
 - Danish
 - Danish with foreign background
 - Foreigner
12. Are you religious?
 - Yes
 - No
 - I don't know
13. What is your profession? _____ and how many hours do you work on a weekly basis? _____
14. How many years of education have you had? (58)
 - < 10 years
 - High school or other 10-12 years
 - Bachelor or other 13-15 years
 - University or other 15-17 years_
 - PhD or other > 18 years
15. What is the total income of your household b. tax? (58)
 - <200.000DKR
 - 200.000-350.000DKR
 - 350.000-750.000DKR
 - >750.000DKR
16. Has a health care professional ever given your child the diagnosis hypermobility? yes / no
17. Does your child have a measured/known vitamin D insufficiency? yes / no
18. Has your child been vaccinated (once or more) against HPV (Human Papilloma Virus)? yes / no
19. Has your child received physiotherapy in the past 6 months for the current pain condition? yes / no
20. Do you believe your child feels anxious or depressed? yes / no
21. Do you believe your child has low self-esteem? yes / no
22. Have you accepted your child's pain condition? yes / no
23. Would you like the general practitioner to give your child pain medication? yes / no
24. Why did your child visit the doctor with his/her pain condition? You may circle more than one answer.
 - For pain relief
 - My child is worried for the cause of pain
 - I am worried for the cause of pain
 - Family pressure/encouragement
 - The pain condition is a personal problem for my child
 - The pain condition is my personal problem
 - My child is due to the pain condition not able to use his/her body as usual
25. Is your child rather solitary? y/n Does he/she tend to play alone? y/n Does he/she have at least one good friend? y/n Is he/she generally liked by other children? y/n Is he/she picked on/bullied by other children? y/n Does he/she get on better with adults than with other children? Mark y or n to all.

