Musculoskeletal pain in adolescents is much more persistent than commonly appreciated. It has previously been described as a self-limiting condition(11), but several studies indicate otherwise. In a cohort study of 564 11-year olds with weekly MSK pain, 50% of the participants still reported pain after one year(12). Prospective cohort studies of adults in general practice show that 16-32% of patients with knee pain still have pain after a year(11, 13). In accordance with this, Kastelein et al. found that 21% of 12 to 35-year-old patients had knee pain six years after initial general practitioner (GP) contact(11). Collectively, these studies highlight that a significant proportion of adolescents will continue to report pain even years after the initial onset of pain.

Can we identify the adolescents with a high risk of MSK pain at follow-up? Our recent systematic review on children and adolescents with MSK pain indicates that female sex, depression, anxiety, and parental pain are associated with a higher risk of MSK pain at follow-up(14). However, the validity of these prognostic factors may be questioned as they have been tested in single cohorts and not validated in new external cohorts. Moreover, in accordance with our results, other studies identify emotional problems, psychological symptoms, and frequent exercise associated to a higher risk of MSK pain at follow-up(13, 15, 16). Huguet et al. reports low to very low quality of evidence for the association between female sex, depressive feelings, frequency of pain, participation in sports and type of MSK pain and prognosis(17). Given the paucity of high-quality evidence for prognostic factors in childhood and adolescent MSK pain, robust studies are needed to further explore prognostic factors in this population(17). We want to follow up on this need and conduct a cohort study with a similar aim as in our review; to investigate prognosis in youth MSK pain. In this cohort study, we will limit our participant group to those who are 8-19 years old, because our participants have to be able to provide self-reported data on a questionnaire. We will not include participants aged 0-7 years as they will have difficulties in doing so and because they i) only represent 2% of all patients consulting GPs in Denmark, with a musculoskeletal complaint(18) and ii) were sparsely represented in our systematic review which included a total of 23.933 patients(14).

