The GP screens the schedule for the day, and indicates eligibility with the word **MSK** written next to the patient name.

When consulting a patient with the indicated **MSK**, the GP is reminded to hand the patient the patient material. This can be done, prior, during or in the end of a consultation while the patient is getting dressed.

The patient hands in the completed questionnaire to an employee of the clinic, who stores it in a locked place. NP or her assistant will collect this in agreement with the clinic.

It is also possible for the GP to include a patient if MSK pain comes up during the consultation, without prior mentioning and hence unknown by the employee.

We will recruit patients from September 2018 to December 2019 and expect 500 participants in the ChiBPS cohort. If we are not able to recruit the number of participants according to our sample size calculations recruitment will continue until this number is reached.

Recruitment of parents

The child must first be included in the study in order for his/her parent(s) to be eligible. For included children, we will also request data from parents during a time window of two weeks from the time of Part-Quest receipt. We are not selective as to if and how many of the parents wish to participate. Parents declining participation will not cause withdrawal of the child's eligibility or inclusion.

Contingency plan for recruitment

A tracking data base will be developed to facilitate tracking and accurate reminders to the clinics included. In the process of initial contact with the clinics, a number of expected included participants will be estimated by each clinic. The clinic will make this estimate based on its patient demography,

which can be different across clinics e.g. some clinics will have a majority of young patients and others the opposite. This number will indicate a minimum for successful recruitment.

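### Pare-Quest item 8 records only the responding parent's chronic pain, so when one form is returned and the parents differ, the child's value depends on who filled it in

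*Protocol*

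**What the plan says.** The introduction of the protocol reports, from the sponsor's systematic review, that "female sex, depression, anxiety, and parental pain are associated with a higher risk of MSK pain at follow-up". It goes on to argue for including parent characteristics.

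Parental pain is measured in one place, Appendix 3 (Pare-Quest), item 8: "Have you experienced chronic pain of more than 6 months, associated with arthritis, migraine, cancer, stomach ulcers or in your muscles, bones or tendons". The answer is yes or no and concerns the person filling in the form.

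The section on recruitment of parents leaves the number of respondents open: "We are not selective as to if and how many of the parents wish to participate". It also keeps children with no parent form: "Parents declining participation will not cause withdrawal of the child's eligibility or inclusion". It does not say which parent should answer.

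The form records who answered. Item 1 separates mother, father and other. Item 2 ("What is your biological relation to your child") separates biological, step- and adoptive parents. The only item that asks about the other parent is item 5: "What is your relationship status with your child's other parent". It concerns marital and living status, not pain. Item 9 does take a report about other family members from the respondent: "Has one or more of your child's siblings had pain in their muscle, joint, bone or tendon".

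**The concern.** The factor is named at family level but measured at respondent level. Take a family in which only the mother has chronic pain. If the father alone returns a form, the record is no. If the mother alone returns one, it is yes. If both do, there is one yes and one no. The child is the same each time.

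The third case is a coding matter that an analysis plan can settle. The first is not, because the mother's status was never asked. If pain in either parent is the factor of interest, such children sit in the unexposed group and pull the odds ratio towards 1. A weak or null result for parental pain could then reflect the form rather than the factor.

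**Working it through.** The plan states no figure for parental pain, so there is none to reproduce. The first step is a reading of the form; the second is an illustration built on assumptions.

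**Who is affected, by reading**

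| Forms returned | Parents agree on pain status | Parents differ |
|---|---|---|
| None | missing | missing |
| One | same value whoever answers | value depends on who answers |
| Both | both forms agree | both statuses known; a coding rule is needed |

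Only the one-form, differing-parents cell holds a value that is wrong for an either-parent definition and cannot be put right later.

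**Size, if pain in either parent is meant**

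Assumptions, none of them in the protocol: prevalence p per parent of 20–40%; within-couple correlation k of 0–0.2; two parents per child; one respondent chosen at random; the same effect whichever parent is affected; outcome risk 45% in truly unexposed children; true odds ratio 2.0 or 1.5.

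Formulas:
- Both parents affected: B = p² + k·p(1−p)
- Either parent affected: A = 2p − B
- Parents differ: D = 2(p − B)
- Share of exposed children found by one form: S = p / A
- Truly exposed share of children recorded as no: F = (A − p)/(1 − p)
- Risk among those recorded as no: F·r₁ + (1 − F)·0.45, where r₁ is the risk in exposed children

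Worked case, p = 0.30, k = 0:
- B = 0.09; A = 0.60 − 0.09 = 0.51; D = 2 × 0.21 = 0.42
- S = 0.30/0.51 = 0.588
- F = 0.21/0.70 = 0.30
- True odds ratio 2.0: odds in the unexposed 0.45/0.55 = 0.818; in the exposed 1.636, so r₁ = 0.621. Risk among recorded no = 0.30 × 0.621 + 0.70 × 0.45 = 0.501, odds 1.005. Observed odds ratio = 1.636/1.005 = 1.63.
- True odds ratio 1.5: the same steps give 1.33.

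Over the range:

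| p | k | Parents differ | Exposed children found by one form | Odds ratio 2.0 seen as |
|---|---|---|---|---|
| 0.20 | 0 | 32% | 56% | 1.74 |
| 0.30 | 0 | 42% | 59% | 1.63 |
| 0.40 | 0 | 48% | 63% | 1.52 |
| 0.20 | 0.2 | 26% | 61% | 1.79 |
| 0.30 | 0.2 | 34% | 64% | 1.70 |
| 0.40 | 0.2 | 38% | 68% | 1.61 |

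At a lower prevalence of 10%, one form still finds only 53–58% of exposed children, but the odds ratio is barely affected (1.87–1.89), because few of the children recorded as no are exposed.

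These figures are for one-form families. If, say, half of families returned both forms, the share found in the worked case would be 0.5 × 1 + 0.5 × 0.588 = 79%.

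**The case against.** The strongest objection is that either-parent pain is not the protocol's stated target. The text says only parental pain, and the sources for the factor and for item 8 are not at hand. If they measured the responding parent's own pain, item 8 captures it as intended and a single form loses nothing. This stands: the size above depends on the assumed target.

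Second, a reader might infer that every one-form family whose other parent has pain is misclassified. That is too strong. Where the respondent also has pain, the recorded yes is correct under an either-parent definition; in the worked case that is 30% of those families.

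Third, a reader might infer that a factor the study set out to replicate is compromised. The replication rationale under sample size names female sex, disability index, multisite pain and HFAQ, and Appendix 5 uses sex and sleep. Parental pain is in neither; the introduction names it as associated but questions how well such factors have been validated.

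Fourth, much can be left to the analysis plan: how to combine two differing forms, how to handle the greater chance that a two-form child scores yes, and whether to analyse by respondent type. Items 1 and 2 allow, for example, an analysis of maternal pain. That stands, but it changes the factor and drops families in which the mother did not answer. It does not restore pain in either parent.

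Fifth, self-report is better than proxy report, and siblings are asked about by proxy only because they do not fill in the form. That is fair, but the proposed line keeps the self-report and adds to it.

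**Conclusion.** The point holds as a gap in the instrument. Item 8 covers the respondent alone, the responding parent is not fixed, and the other parent's pain is not asked, so in one-form families with differing parents the recorded value depends on who answered.

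Its size is conditional. With either-parent pain as the target and the assumptions listed, one form finds about 56–68% of exposed children and an odds ratio of 2.0 appears as about 1.5–1.8. A higher share of two-form families shrinks this.

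A reader might also infer that the exposure is distorted by socioeconomic status through the number of parents responding. That is plausible, but the documents give nothing on who responds, and education, income and living arrangements are recorded and can be adjusted for.

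The point concerns one candidate predictor. The primary outcome and the sample size are untouched. It merits action because the repair is cheap and has to be made when the data are collected.

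**What to change.** Keep item 8 as it stands and add one line below it: 'Has your child's other parent experienced such pain? yes / no / don't know'. Define parental pain at child level as yes if either parent is reported to have it on any returned form, and keep the respondent's own answer as a separate variable so that a respondent-level or maternal analysis remains possible. State in the protocol which of the two is the intended factor.

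The cost is one line on the parent form and its translation. The downside is some proxy error and some don't-know answers, probably more often in separated families; item 5 allows that to be examined.

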As mentioned in FINER, this study is approved by the National Ethics Committee (NVK). Declarations of consent, provided by NVK will be collected from included participants and parents(28). Below are listed, declaration and participant age groups on which the declarations apply to.

- *Participants 18 - 19 years of age*: declaration S1 (Danish, not included).
- *Participants 8 – 17 years of age*: declaration S5, (Danish, not included) deputy consent to be provided by the holder of custody of the participant. As we have no intervention or invasive testing in our study, one parental signature is sufficient.

Interventions

We have no interventions for this study.

Recruitment process

Recruitment of GP clinics

Our aim is to recruit a sample that represents the Danish child and adolescent population with musculoskeletal pain. For this purpose, we will invite GP clinics across Denmark through random recruitment procedure using random.org. Initially, we will recruit patients from a selected group of GPs, also representing the Danish child and adolescent population. Random recruitment will follow, and be based on experience from recruitment of the initial selected group. We recruit from an unselected list of GPs from across the country, and thereby invite a heterogeneous patient population in terms of mean income, mean life expectancy, and no. of GP visits etc.

Assuring optimal recruitment of GP clinics

According to Solberg LI 7 *R-factors* are important in the recruitment process and obtaining data(34). We will apply these on our recruitment process as follows:

Relationship: between the first author NP (a medical doctor, GP-trainee and clinician) and her physician-peers. NP will make first contact to the GP clinics and offer to visit or meet on Skype, if necessary. A direct recruitment of clinicians by clinicians is a successful component of recruitment of clinicians(34).

Reputation: NP is among her physician-peers known as a clinician and a researcher.

Requirements: for participation in our project is at a tolerable and moderate level and the GP decides whether to recruit patients or have an employee doing this.

Rewards: We compensate the GPs for their participation as datacollectors, with a fixed amount per included patient. This according to regulation §3 by The Committee of Multipractice Studies in General Practice(35).

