2. carrying your school bag to school

3. sitting on a school chair for a 45 min. lesson

4. standing in a queue for 10 min.

5. sitting up in bed from a lying position

6. bending down to put your socks on

7. standing up from an armchair at home

8. running fast to catch a bus

9. sport activities at school

11) Tired during the day (42, 45).

Sample-size

The sample-size in this study was determined using the two following rationales: 1) a sample-size large enough to test and replicate the analyses from previous studies on. Given the prior odds (0.5, 1, 2) of follow-up MSK pain for patients, using estimates for the prognostic factors female sex, high disability index, multisite pain, and maximum HFAQ from our systematic review(14). We gained an estimate of P-values according to sample size, for all factors individually (Appendix 8). Sample size of 500 patients, would result in an estimate of P-values below 0.05 for all prognostic factors and 2) investigate a range of new prognostic factors related to the sparsely investigated ethnicity and socioeconomic status. As no one has yet tested any of these potential important prognostic factors, and never in a general practice setting, we decided on 500 subjects. The 500 subjects was decided based on 250 cases (we assume 50% will continue to experience pain at our primary follow-up time) giving approximately 125 cases per prognostic factor (500/number of prognostic factors). The results from this analysis will be considered as explorative as no studies have previously been conducted in a general practice setting. Again, assuming 50% has pain at follow-up and 20 events for each to be tested factor are needed. The model should allow for 10-15 variables in a multivariable logistic regression analysis. This would lead to a sample size of 480. Assumed, 5% is lost to follow-up and we have a sample-size of 504 included participants. Given the high prevalence of MSK pain at follow-up, this sample-size is feasible to include.

Questionnaires

We use three questionnaires in data collection of patient and parent characteristics: participant baseline questionnaire (Part-Quest-base) (Appendix 1), participant follow-up questionnaire (Part-Quest-follow-up) (Appendix 2), and the parent questionnaire (Pare-Quest) (Appendix 3).

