In relation to our study, all these factors have an interest as to whether they present as prognostic factors in MSK pain at follow-up. We questioned whether it would be ethical to ask the question “Do you feel Danish?”, why we conducted an intern survey among a group of seven immigrants and one descendant, representing five countries, from Europe and the Middle East. Among the immigrants, only one felt offended by this question. The rest did not, but two out of these said they would have felt offended, if they were born in Denmark. The descendant was not offended by the question. We decided to keep this question as part of our questionnaire and keep it applicable for all participants including the ethnic Danes, because we can't presuppose this patient groups' answer to this question. Hence the answer is a potential prognostic factor.

The questionnaires will be pilot tested among target participants; Part-Quest among 8-19-year-olds with MSK pain and the Pare-Quest among parents to children with MSK pain.

Translation of questionnaires

Our questionnaires will be cross-cultural adaptive for participants with poor Danish language skills, insufficient to comprehend the original Danish questionnaires. In the process of translation and validation, we will translate our questionnaires both linguistically and culturally. Our three questionnaires and our bulletin will be translated from English to Danish, which is the mother tongue of the majority of our prospective participants.

The Part-Quest, Pare-Quest, and The Faces Pain Scale Revised (FPS-R) will be translated into Danish, following the general methodology of translation, back-translation, and verification (46):

1. English to Danish. Translation by a pool of 5-7 researchers fluent in English and Danish, with the latter as their mother tongue.
2. The Danish version will be read by 3-4 teachers, nurses, or physicians who are all familiar with young children's use of language, to ensure suitability for children 8-11 years of age.

3. The Danish version will be back-translated into English by a bilingual person who does not know anything about the questionnaires and has not seen the original version. The original and the back-translated versions will be compared and needed adjustments will be made.
4. The Danish version will be pilot-tested with 2-3 children 8-11 years of age.

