Hereafter, data will be extracted from REDCap and transferred to a table similar table 1, which will then be anonymized through participant ID.

Statistical methods

Descriptive results will be stratified by sex and MSK pain type, presented with their central estimate and appropriate measure of dispersion (95% confidence interval CI). All descriptive statistics and test will be reported in accordance to the recommendations of the STROBE statement(29).

We will test the univariate association between each potential prognostic factor as well as combining the factors in a multivariable model to show the individual contributions.

The primary analysis will be done on those who has a first time consultation with their GP concerning their current MSK pain, but all consultations will be included.

The full statistical analysis plan will be developed concurrently and will be finalized before the last patient is enrolled. We minimize information bias by using identical questionnaires for all patients included, e.g. by asking both Danes and non-Danes whether they feel Danish or not.

Ethics and dissemination

The Ethics Committee of the North Denmark Region has waived the need for ethical approval of this study (date 090617). The Multidisciplinary Committee has approved the study and recommends Danish GPs to participate (ID: MPU 20-2017 / date 100117). We are currently applying their grant, to provide compensation to the included GPs for every recruited participant they provide to the study. The Danish Data Protection Agency has similarly granted access to the project (date 101717). All mentioned reviews are executed prior to protocol registration in ClinicalTrials.gov and to enrollment of the first participant (figure 1).

The adolescents included in the ChiBPS cohort will receive usual care, i.e. as usually administered at their GP. This study will not intervene in the diagnostic and therapeutic process.

The manuscript will be submitted for publication in an appropriate peer-reviewed journal. In addition to this we will produce material for distribution among general practitioners and other healthcare providers managing children and adolescents with MSK pain. This will be done by data visualization through social media, websites and patient associations. The included participants will also be offered knowledge sharing of study results, if interested.

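### The yes/no vitamin D item pools untested children with children who tested normal, so the factor partly reflects who was tested, to an unknown degree

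*Protocol*

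**What the plan says.** Item 17 of the parent form (Protocol, Appendix 3) reads "Does your child have a measured/known vitamin D insufficiency? yes / no". Those are the only two answers. No item on the baseline, follow-up or parent form asks whether vitamin D was ever measured.

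The study does not supply the missing information. Under Declarations of consent the protocol says: "As we have no intervention or invasive testing in our study, one parental signature is sufficient". Under Ethics and dissemination it says: "This study will not intervene in the diagnostic and therapeutic process". Whether a child is tested is thus decided in usual care and not recorded.

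On the use of questionnaire items, the Questionnaires section says that "all these factors have an interest as to whether they present as prognostic factors in MSK pain at follow-up". Statistical methods adds: "We will test the univariate association between each potential prognostic factor", followed by a multivariable model. Vitamin D is not named in these sentences or in the exposures listed under Outcomes. Table 1, which assigns roles to the assessments, cannot be read in the copy reviewed.

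The protocol states no testing rate and no prevalence of insufficiency.

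**The concern.** A candidate prognostic factor should have a reference group whose meaning is known. Here 'no' holds two different groups under the same tick, and no analysis of the returned forms can separate them.

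Two errors can follow. If insufficiency is truly prognostic, untested insufficient children in the 'no' group pull the odds ratio towards 1. If testing tends to follow longer or more severe pain or earlier consultations (plausible, but not stated in the protocol), 'yes' also marks earlier work-up, and the item can look prognostic when vitamin D status plays no part. The two errors act in opposite directions, and the data could not show which is at work.

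**Working it through.** **1. What each answer can mean**

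| State of the child | Answer available to the parent |
|---|---|
| Tested, too low | yes |
| Tested, normal | no |
| Never tested | no, or left blank |

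A format limit does not explain the two-way answer. The parent form's item on religion has a don't-know answer, as do several participant items.

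**2. Attenuation, worked example**

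The plan has no vitamin D figure to reproduce. From the protocol: 500 children, and an OR of 1.78, which Appendix 5 uses for sex and is borrowed here for scale. Assumed: tested t = 10% at random, insufficient d = 30%, risk of pain at follow-up if sufficient p0 = 0.45, and all untested children answered 'no'.

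- Recorded 'yes' = 500 × 0.10 × 0.30 = 15; recorded 'no' = 485.
- Insufficient but untested = 500 × 0.30 × 0.90 = 135; 135/485 = 28% of the 'no' group.
- Odds if insufficient = 1.78 × 0.45/0.55 = 1.456, so p1 = 0.593.
- Risk in the 'no' group = (135 × 0.593 + 350 × 0.45)/485 = 0.490; odds 0.960.
- Observed OR = 1.456/0.960 = 1.52.

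Over tested 5–40% and insufficient 20–50%, there are 5 to 100 'yes' answers, 13–49% of the 'no' group are in truth insufficient, and the observed OR is 1.35 to 1.65.

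A second set of assumptions was also run: tested 10–80%, insufficient 10–50%, testing equally or twice as likely in insufficient children, true OR 2, reference risk 40%. A true OR of 2 then appears as 1.44 to 1.99. Never-tested children form 91–96% of the 'no' group if 10% are tested, and 22–33% if 80% are.

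**3. The opposite error**

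Suppose insufficiency has no effect, but being tested carries OR 2 and the untested risk is 40%. With t = 10% and d = 30%:

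- Odds if tested = 2 × 0.4/0.6 = 1.333, risk 0.571.
- Risk in the 'no' group = (0.07 × 0.571 + 0.90 × 0.40)/0.97 = 0.412; odds 0.702.
- Observed OR = 1.333/0.702 = 1.90, with no vitamin D effect at all.

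Over the second set of ranges this spurious OR runs from 1.16 to 1.95.

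**4. Does the item track testing or insufficiency?**

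A 'yes' needs both a test and a low result. For A = tested or A = insufficient, the correlation is phi = √[P(yes)(1 − P(A)) / (P(A)(1 − P(yes)))]. It is larger for whichever condition is rarer.

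- Tested 10%, insufficient 30%: phi 0.53 with testing, 0.27 with insufficiency.
- Tested 50%, insufficient 10%: phi 0.23 with testing, 0.69 with insufficiency.

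**5. Would restricting to tested children be better?**

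In the example of step 2, on the log OR scale:

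- 15 'yes' against 485 'no': bias = ln 1.52 − ln 1.78 ≈ −0.16; SE ≈ 0.53; mean squared error ≈ 0.28 + 0.03 = 0.31.
- 15 too low against 35 measured normal: no bias under these assumptions; SE ≈ 0.63; mean squared error ≈ 0.39.

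Restriction removes the bias but costs more in precision than it gains.

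**The case against.** The strongest defence is that the item asks about a known insufficiency, and for that history 'no' is correct for an untested child. The study looks for descriptive variables associated with later pain and usable in general practice; it does not set out to estimate the effect of vitamin D status. The hypermobility item just above likewise records a diagnosis given. This stands in part. The factor is usable if it is labelled as known insufficiency, but the protocol gives no such label, and nothing stops a reader taking 'no' as sufficient.

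Second, likely drivers of testing are collected (consultation number, pain intensity and duration, country of birth), and a multivariable model is planned. Adjustment may reduce confounding. It cannot split the 'no' group.

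Third, vitamin D is not a named exposure and plays no part in the sample size, and parents may decline to take part. That limits the weight of the point. In the worked example the bias is also only about 0.3 of a standard error (0.16/0.53).

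A reader might infer more than the documents support:

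- **That the item mainly measures who was tested.** This requires fewer children tested than insufficient, and the protocol gives neither figure. Step 4 shows that it can go either way.
- **That an untested child's parent must answer 'no'.** The item can be left blank.
- **That testing status is lost for good.** The research assistant phones the participant or parent after collecting the form, and follow-up questionnaires go to participants and parents by e-mail.

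**Conclusion.** The point holds in a limited form. Item 17 pools tested-normal with never-tested children, so as a prognostic factor it partly reflects who was tested, to an unknown degree, and cannot be read as vitamin D status. That follows from the form alone.

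Its size rests wholly on assumed testing rates, prevalence and effects. Under those used here, a true OR of 1.78 appears as 1.35 to 1.65, and a spurious OR of 1.16 to 1.95 can arise from testing alone when testing carries OR 2. The net direction is unknown.

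This concerns one exploratory item. The primary outcome and the sample size are unaffected. It merits correction because the change is small and the yes/no answers alone cannot be repaired by analysis.

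**What to change.** Change the answers to item 17 to: 'Yes, measured and too low' / 'Measured and normal' / 'Never measured' / 'Don't know'. Put the same question, referring to the time of the parent form, to families who have already returned the yes/no version, at the next planned contact.

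Keep all children in the analysis, with never measured or don't know as its own category. Report too low against measured normal as a supplementary contrast only, because step 5 shows what restriction costs in precision. Where only yes/no exists, label the factor 'known (diagnosed) insufficiency' and do not interpret 'no' as sufficient.

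The cost is two more tick boxes with their translations. The drawback is that the measured-normal category may be sparse (35 of 500 in the worked example), so the supplementary contrast will be imprecise.
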